5.3.1.1.3 ODM-208 with corticosteroid replacement therapy in Part 1B (added in Amendment 4)

In the morning of Day 1 (Visit 1), a single dose of ODM-208 is given with a glass of water within 30 min after meal concomitantly with an oral glucocorticoid (dexamethasone once daily or prednisone/prednisolone twice daily or hydrocortisone three times daily) and fludrocortisone 50  $\mu$ g once daily.

In 24 hours after the single dose of ODM-208, repeated daily dosing of ODM-208 will be started with corticosteroids.

Note: In case the patient forgets to take any of the corticosteroid doses, it should be taken as soon as possible.

5.3.1.1.4 ODM-208 dose selection

The dose level for Cohort 2 and all further cohorts in Part 1A will be decided by the SMB after a minimum of 3 patients have provided evaluable data on the previous dose level. The maximum allowed incremental increase can be 100% of the dose in the previous cohort in absence of

toxicity. Patients who do not experience any DLT within 24 h of the first dose will continue with repeated administration of the same dose for at least 12 weeks. Dosing of the second patient in each cohort in this part can start only after the first patient in the cohort has completed 14 days of repeated dosing and safety data from the first patient is evaluated. Dosing of subsequent patients in the same cohort can start from at least 24 h after the dosing of previous patient (see section 3.1.1).

The highest achieved individual exposure level (AUC0-24 36 500 h\*ng/ml) in 28-day toxicology study in dog is considered the initial maximum clinical exposure level of ODM-208 which should not be exceeded in phase I dose escalation. The number of cohorts is dependent on clinical exposure levels of ODM-208.

The dose level(s) of ODM-208 and replacement therapy and the dosing schedule(s) in Part 1B will be decided based on data from Part 1A. The dose selected for Part 1B will not exceed the highest tolerated dose given in Part 1A.

The dose and the dosing schedule in Part 2 of the study will be decided based on the data collected in Part 1. The dose selected will not exceed the highest dose administered in Part 1.

If deemed necessary to achieve better absorption, antitumour activity, and depending on the observed PK, PD and safety, the SMB can decide to modify the conditions for dosing schedule (e.g. dosing without food).

# 5.3.1.2 Part 2/Phase 2

In Part 2 ODM-208 is taken orally at 5 mg twice daily (total daily dose 10 mg) with a glass of water within 30 min after meal concomitantly with once daily oral dexamethasone 1.5 mg (recommended starting dose) and fludrocortisone 100 µg (starting dose) in the morning, with the possibility to titrate the dexamethasone and fludrocortisone doses if necessary. In case 5 mg twice daily is not tolerated by a subject the dose may be reduced (for example by reducing dose frequency).

# 5.4 Method of assigning study subjects to treatment groups

The patients will enter the study in the order they are found to be eligible. They will receive their patient numbers in the order they enter pre-screening.

# 5.5 Blinding

This is an open-label study.

# 5.6 Emergency procedures

# 5.6.1 Treatment of emergencies

Emergencies will be treated according to the decision of the physician in charge or the investigator, when available.

At the event of an acute adrenal crisis or if patient deteriorates while using increased doses of glucocorticoid therapy, the patient must be admitted to a hospital and parenteral corticosteroid

treatment and rehydration should be started. The initial work-up should consist of imaging and blood tests including common tests for infections, blood glucose, complete blood cell count, C-reactive protein (CRP), creatinine, creatine kinase (CK), sodium, potassium, cortisol, ACTH, TSH, free T4, phosphate, and calcium and, other tests considered necessary. This diagnostic work-up should not overly delay the start of the treatment for acute adrenal insufficiency.

Acute adrenal crisis is managed according to the institutional hospital emergency room guidelines which should not deviate from the published consensus guidelines (Arlt W et al., 2016). The guidelines recommend that the management starts with a rapid 1000 ml intravenous (i.v.) isotonic saline rehydration and a bolus of hydrocortisone 100 mg i.v. This is followed by hydrocortisone given either 200 mg as a 24h i.v. infusion or alternatively, 50 mg q.i.d. Further intravenous rehydration during the initial 24h. Tapering of the i.v. hydrocortisone dosing may start the following day by reducing the dose of hydrocortisone to 50 mg b.i.d. When hydrocortisone is given at the dose of 50 mg/day or greater, fludrocortisone administration may be on hold. ODM-208 should be on hold until the patient's condition has been stabilised and the i.v. hydrocortisone dose is less than 50 mg/day (Arlt W et al., 2016).

Tapering of i.v. hydrocortisone dose and reinstituting to an oral regimen can be started after clinical recovery. During the following days after the parenteral hydrocortisone has been stopped the patient is at a risk of reoccurring glucocorticoid insufficiency and therefore all patients should be followed up carefully. If there was an identifiable factor causing abnormal stress, the same glucocorticoid dose as was used previously can be used also after recovery. If the crisis was deemed to be a result of inadequate basal glucocorticoid supplementation and no identified stress factor was present, the glucocorticoid supplementation dose may be increased, or the glucocorticoid may be switched to another glucocorticoid at the discretion of the investigator after discussions with the Sponsor.

Patients and their family members must be instructed to promptly inform the emergency department and other medical personnel about the study treatment-related adrenal insufficiency and the need for constant glucocorticoid and mineralocorticoid replacement therapy. Additional doses of corticosteroid and steroid emergency card for treatment-related adrenal insufficiency will be provided for patients.

Management of adrenal insufficiency is presented in Appendix 2A and Measures to prevent adrenal crisis in Appendix 2B.

# 5.7 Prior and other concomitant treatments

All prior lines of therapy for prostate cancer (e.g. primary therapy, hormonal therapy, type of radiation therapy and surgery) must be recorded on the CRFs.

All other concomitant treatments (including blood transfusion) taken during the study from the date of signing the IC until the EOS visit must be recorded on the CRFs for concomitant treatments. Additionally, any unplanned diagnostic, therapeutic or surgical procedure performed during the study must be recorded on the CRFs.

# 5.7.1 Mandatory treatment during the study

Patients who have not undergone bilateral orchiectomy and are receiving GnRH therapy prior to the study must continue the GnRH therapy during the study.

# 5.7.1.1 Recommended treatments during the study

Since both castration therapy and glucocorticoid replacement treatment are associated with an increased risk of bone loss especially during long-term use, bone loss preventing therapy is highly recommended for all patients. All patients should use oral calcium and vitamin D supplementation during the study. If needed according to the judgment of investigator, prophylaxis for opportunistic infections such as pneumocystis pneumonia (PCP) is recommended (Added in Amendment 4).

For Part 1 only: For patients treated with a higher glucocorticoid dose than the equivalent of 40 mg of hydrocortisone, proton-pump inhibitor (PPI) therapy (e.g. pantoprazole) is recommended.

# 5.7.2 Permitted treatments during the study

Any treatments that are considered necessary for the patient's welfare and which will not interfere with the study treatment, with the exceptions listed in Table 1, may be used at the discretion of the investigator.

Granulocyte colony stimulating factor (G-CSF) and other haematopoietic growth factors may be used when clinically indicated. Palliative radiotherapy is allowed during the study.

Topical steroids and inhalation steroids are permitted.

If the permissibility of a specific treatment is questionable, the investigator must consult the medical monitor.

# 5.7.3 Prohibited treatments during the study

Systemic use of strong CYP3A4 inducers, P-gp inhibitors and aldosterone agonists is not allowed concomitantly with ODM-208. Prohibited treatments are listed in Table 1.

1 able 1. FIOIDDIED Systemic deadlients during the study	Table 1.	Prohibited	systemic	treatments	during	the study
--	----------	------------	----------	------------	--------	-----------

Prohibited concomitant medication	Comments					
Aldosterone antagonist	E.g. spironolactone, eplerenone, canrenone, potassium canrenoate					
Other investigational agents						
Any treatment affecting GI motility significantly as judged by the investigator (Part 1 only)	E.g. cisapride					
Antacids	From 2 h before dosing until 4 h after dosing during days when PK samples are collected.					

 
Strong CYP3A4 inducers, e.g.:
 
avasimibe, carbamazepine, lumacaftor, phenobarbital, phenytoin, rifampicin, rifapentine, St John's Wort
 
P-gp inhibitors: 
 
erythromycin, clarithromycin, rifampicin
 
ketoconazole, itraconazole, posaconazole
 
artesunate-pyronaridine
 
ritonavir, indinavir, nelfinavir, atazanavir
 
glecaprevir-pibrentasvir, simeprevir, ledipasvir-sofosbuvir
 
verapamil, diltiazem
 
dronedarone, propafenone, quinidine
 
cyclosporine, valspodar, milk thistle (Silybum marianum)
 
 
 
	Listed P-gp inhibitors may lead to increased ODM-208 plasma concentrations. These medications have been shown to change AUC > 200% for some co-medications. Data obtained from the University of Washington Drug Interaction Database (DIDB).					

# 5.7.4 Precautions

The preliminary studies using human recombinant CYP enzymes suggest CYP3A4 participates in the oxidative metabolism of ODM-208. Dexamethasone, hydrocortisone, prednisone and fludrocortisone are also mainly metabolised by CYP3A4. In addition, the preliminary studies have indicated that ODM-208 is a P-gp substrate. Thus, drug-drug interactions with CYP3A4 inhibitors, CYP3A4 inducers and P-gp inhibitors may occur. The use of strong CYP3A4 inducers and P-gp inhibitors is prohibited during the study (Table 1). Use of strong CYP3A4 inhibitors should be avoided if possible. Based on in vitro metabolic clearance data the effect of the CYP3A4 inhibitors on the exposure of ODM-208 is expected to be mild.

**US and Finland only:** A special precaution should be used when patients receiving HIV medication (antiretroviral therapy) are enrolled due to possible drug-drug interactions with ODM-208 and dexamethasone.

Fluid volume of patients may change due to changes in mineralocorticoid status, and therefore diuretics and beta-blockers should be used with caution (see Appendix 2C).

# 5.8 Restrictions

Consumption of grapefruit or grapefruit juice, and use of liquorice should be avoided from the screening visit until the EOS visit.

# 5.9 Treatment compliance and exposure

Treatment compliance of ODM-208 will be assessed at each visit by study treatment accountability and diary. Patients are requested to return all study treatment packages (unused study treatments and empty packages) at every visit.

Any treatment deviation must be recorded. The patient should be asked about the reason for noncompliance.

Drug accountability records will be kept. The investigator must maintain accurate records demonstrating the date and amount of study treatments received, to whom and by whom dispensed (drug dispensing list) and accounts of study treatments accidentally or deliberately destroyed.

At the end of the study, any remaining study treatments will be collected and returned to the sponsor. Any discrepancies between the returned and expected returned study treatments should be explained.

# 5.10 Availability of ODM-208 after termination of study

There is no option to continue ODM-208 treatment therapy once the patient has discontinued the study. Subsequent treatments of the patient will be at the discretion of the attending physician.

# 6. STUDY PROCEDURES AND ASSESSMENTS

# 6.1 Study procedures

# 6.1.1 Part 1/Phase 1

Table 2 lists all Part 1 study procedures and indicates with an 'x' during which visit a particular procedure is performed.

Assessments during Visit 1 and Visit 2 are presented in Table 4 and Table 5.

# Table 2.Part 1/Phase 1: Schedule of study events

Visit	Pre- screening	Screening	11	2 	3	4	5	6	7	8	9	10	11	12	13, 14 etc.	Post- treatment visits	EOS	Follow -up 
Day		-21 to -1	1, 2, 3	8	15	22	29	43	57	71	85	113	141	169	253, 337 etc.	+7, +14, +21	+28	
Window (days)				± 2							± 4					± 2	± 4	
Week				1	2	3	4	6	8	10	12	16	20	24	36, 48 etc.			
AR mutation pre-screening IC and blood sample 	х																	
Informed consent		х																
Eligibility criteria and decision of entry		х																
ODM-208 administration 			х															
Glucocorticoid administration 			X													х		
Fludrocortisone administration 			x 															х
Telephone contacts between visits (inquiry of symptoms)				x 														
Demography, height and medical history		х																
Physical examination and body temperature		х	х	x	x	x	х	х	х	x	x	х	х	х	х	х	х	х
Weight		х	х	x	x	x	х	x	х	x	x	х	х	х	х	х	х	x
Orthostatic test 		x 	х	x	x	x	х	х	х	x	x	х	х	х	х	х	х	х
Supine BP (during PK days)			x 	x														х
HR		x 	х	x	х	х	х	х	х	х	х	х	х	х	х	х	х	х
12-lead ECG		x 	x 	x	x	x	х	x	х	x	x	х	х	х	х		х	
ECOG performance status		х	х	х	х	х	х	х	х	х	х	х	х	х	х			
Safety laboratory assessments (blood and urine)		х	х	x	х	x	х	х	х	x	x	х	х	х	х	x 	х	x 
Blood sample for cortisol, aldosterone			х	x			х				x			х	х	х	х	x
Blood sample for renin			х	x	х		х		х		х	х	х	х	х		х	х
Blood sample for TSH, FT4		х	х						х				х		х			
Blood sample for LH, FSH			х	x			х				х							
Blood for HBA1c (for patients with diabetes)		х									х			х	x		х	

Visit	Pre- screening	Screening	11	2 	3	4	5	6	7	8	9	10	11	12	13, 14 etc.	Post- treatment visits	EOS	Follow -up 
															253,	+7, +14,	+28	
Day		-21 to -1	1, 2, 3	8	15	22	29	43	57	71	85	113	141	169	337	+21		
W/: 1 (1 )															etc.			
Window (days)				±2	1	1	1	1	<del>1</del>	<del>1</del>	± 4	 	r	1	1	± 2	± 4	1
Week				1	2	3	4	6	8	10	12	16	20	24	36, 48 etc.			
Blood samples for PK			х	x			х				x							
Blood samples (aliquots of PK samples) and urine collection for metabolite screening 			x	x			x				x							
Blood sample for PSA		х	х				x		х		x	х	х	х	х		х	
Blood sample for ACTH			х	x			x		х		x			х	х		х	х
Blood sample for testosterone		х	х	x			x				x			х	х			
Blood samples for PD assessments 			x				х				x						x 	x 
Blood sample for plasma protein binding				x														
Blood sample 1 for explorative ctDNA analyses			x														х	
Blood sample 2 for explorative ctDNA analyses			x						х			х		х	x		х	
Blood sample for germline DNA and PG 			x															
Radionuclide bone scan		x 							x 			x 		x 	x 			
Chest, abdomen and pelvic CT or MRI		x 							х			х		х	x			
Dispense ODM-208 and replacement treatment			x				x		х		x	х	х	х	x			
Dispense emergency card and hydrocortisone			v															
emergency kit			х															
Return study treatment							х		х		x	х	х	х	х		х	
Dispense/return diary card			х	x	x	x	x	x	х	х	x	х	х	х	х		х	
AEs, concomitant treatments and current medical conditions		х																

 See Table 4 for details of Part 1 Visit 1
  See Table 5 for details of Part 1 Visit 2

Depending on time needed to taper down glucocorticoid and mineralocorticoid treatment After meal

Confidential

 Started on Day 1

 Telephone calls on Day 5, 12, 19 and 26  $(\pm 1)$ 

3 registrations 1-2 min apart

 Only electrolytes

 Urine to be collected on visit 1 and 2 only.
  Androstenedione, dehydroepiandrosterone sulfate (DHEA-S), pregnenolone, 11β-hydroxyandrostenedione (110HA4), 11-ketotestosterone (11KT)

 Pregnenolone and DHEA-S only
  The sample is used for PG assessment only if patient has signed PG IC
  Previous scans can be used as the baseline assessment if they were performed within 4 weeks prior to the start of the study treatment.

 Performed within 1 week before the actual visit (results must be available at the visit).

 The sample is taken only if patient has signed pre-screening IC.

# 6.1.2 Part 2/Phase 2

Table 3 lists all Part 2 study procedures and indicates with an 'x' during which visit a particular procedure is performed.

# Table 3. Part 2/Phase 2: Schedule of study events

Visit	Pre- screening	Screening	1	2	3	4	5	6	7	8	9	10	11	12	13, 14 etc.	Post- treatment visit	EOS	Follow -up 	Sur- vival 
Day		-21 to -1	1	8	15	22	29	43	57	71	85	113	141	169	253, 337 etc.	+14	+28		
Window (days)				± 2							± 4					± 2	± 4		±14
Week				1	2	3	4	6	8	10	12	16	20	24	36, 48 etc.				Every 12 wks
AR mutation pre-screening IC and blood sample	Х																		
Informed consent		х																	
Eligibility criteria and decision of entry		х																	
ODM-208 administration 			х																
Glucocorticoid administration			X												х				
Fludrocortisone administration			х															х	
Telephone contacts between visits (inquiry of symptoms)				x 															
Demography, height and medical history		х																	
Physical examination and body temperature		х	x	х	x	x	x	х	х	х	х	х	х	х	х	x 	х	x 	
Weight		х	x	х	x	x	x	х	х	х	х	х	х	х	х		х		
Supine BP and HR		x 	x 	х	x	x	x	х	х	х	х	х	х	х	х	Х	х	х	
12-lead ECG		x 	x 	x	x	x	х	х	x	x	x	х	х	х	х		х		
ECOG performance status		х	х	x	x	x	х	х	x	x	x	х	х	х	х				
Safety laboratory assessments (blood and urine) 		х	х	x	x	x	х	х	x	x	x	х	х	х	х	x 	х	x 	
Blood sample for cortisol, aldosterone 			х	x			х				x					х	х	х	
Blood sample for ACTH 			х	x			х				x						х	х	
Blood samples for dexamethasone,																			
fludrocortisone and CBG 			A	X	x	x	X	X	X	X	X								
Blood sample for renin 			х	х	x		х		x		x			х	x		х		
Blood sample for TSH 		х	х								x			x 					

Visit	Pre- screening	Screening	1	2	3	4	5	6	7	8	9	10	11	12	13, 14 etc.	Post- treatment visit	EOS	Follow -up 	Sur- vival 
Day		-21 to -1	1	8	15	22	29	43	57	71	85	113	141	169	253, 337 etc.	+14	+28		
Window (days)				± 2						1	± 4				1	± 2	± 4		±14
Week				1	2	3	4	6	8	10	12	16	20	24	36, 48 etc.				Every 12 wks
Blood for HBA1c (for patients with diabetes) 		х									x			х	x		х		
Blood samples for PK			x 	x 					x 										
Blood sample for PSA 		х	х		х		х		х		х	х	х	х	х		х		
Blood sample for testosterone/other steroids 		х	x	x			x				x			x	x				
Blood samples for androstenedione, DHEA-S, pregnenolone/other steroids 			x	x			x				x						x 	x 	
Blood sample 1 for explorative ctDNA analyses			х														х		
Blood sample 2 for explorative ctDNA analyses			х						x			x		x	x		x		
Blood sample for CTC count 			х								х								
Blood sample for AR-V7 on CTC 			х																
Blood sample for explorative plasma			х		х	x	x												
Blood sample for germline DNA and PG			х																
Radionuclide bone scan		x 							x 			x 		x 	x 				
Chest, abdomen and pelvic CT or MRI		x 							x 			x 		x 	x 				
Dispense ODM-208 and replacement treatment			х				х		х		х	х	х	х	х				
Dispense emergency card and hydrocortisone emergency kit			x																
Return study treatment							x		x		x	х	х	х	х		х		
Dispense/return diary card			x	х	x	x	x	x	x	x	x	x	x	x	х		х		
Digital symptom questionnaire (voluntary) 		×	x 																
AEs, concomitant treatments and current medical conditions		х																	

Visit	Pre- screening	Screening	1	2	3	4	5	6	7	8	9	10	11	12	13, 14 etc.	Post- treatment visit	EOS	Follow -up 	Sur- vival 
Day		-21 to -1	1	8	15	22	29	43	57	71	85	113	141	169	253, 337 etc.	+14	+28		
Window (days)				± 2							$\pm 4$					± 2	± 4		±14
Week				1	2	3	4	6	8	10	12	16	20	24	36, 48 etc.				Every 12 wks
Survival status		X																	X

Depending on time needed to taper down glucocorticoid and mineralocorticoid treatment.

 After meal

 Telephone calls on Day 5, 12, 19, 26, 36 (week 5) and 50 (week 7)  $(\pm 1)$ 

3 registrations 1-2 min apart

 Only electrolytes

 Every 3 months until 6 months, thereafter every 6 months

 Pregnenolone and DHEA-S

 Previous scans can be used as the baseline assessment if they were performed within 4 weeks prior to the start of the study treatment

 Performed within 1 week before the actual visit (results must be available at the visit)

 Local laboratory analysis

 Central laboratory analysis

 For TSH, PSA and testosterone, screening samples are analysed at the local laboratory, whereas the samples from Visit 1 onwards are analysed at the central laboratory

 In day 8, PK samples will be taken predose and 2 h after dose

 In day 57, PK samples will be taken predose

 Physical examination only

 For sampling time points, see Table 6

 Patients will fill in the questionnaire using a digital application at screening (querying the past 7 days) and at home between visits every third day during the first 3 months, and after

that once a week until week 24.

 Digital symptom questionnaire will not be used in France.

-Follow up every 12 weeks at visits or telephone calls with the subject, current physician or local death registries; added in Amendment 12.

# 6.1.3 **Procedures during the pre-screening period**

A potential study subject will receive both written and verbal information about the prescreening, and will have an opportunity to ask questions and sufficient time to decide whether to participate in the AR mutation pre-screening test (optional in Part 1, mandatory in Part 2). Mutations in the LBD of AR in plasma ctDNA will be analysed centrally.

- A signed and dated written AR mutation pre-screening IC will be obtained.
- Blood samples for AR analysis will be taken.
- When results are available, the subject will be contacted to inform him about the results and discuss with him the subsequent steps.

# 6.1.4 Procedures during the screening period - Day -21 to Day 1

A screening visit will take place within 21 days before the first ODM-208 administration at Visit 1 (Day 1). If the subject has an ongoing glucocorticoid replacement treatment, it is important to continue the daily glucocorticoid intake during the whole screening period and to switch it to study replacement therapy on Day 1. A prospective study subject will receive both written and verbal information about the study, and will have an opportunity to ask questions and sufficient time to decide whether to participate in the study. A signed and dated written IC(s) will be obtained.

The following procedures will be performed at the screening visit to ensure that all the inclusion/exclusion criteria are met:

- Demographic data will be recorded.
- Physical examination, body temperature, weight and height will be recorded.
- Medical history will be recorded.
- Orthostatic test (Part 1 only) see section 6.5.4.1), BP, heart rate (HR) and 12-lead ECG will be recorded. ECG, BP and HR will be recorded after 10 min rest in supine position (3 consecutive registrations 1-2 min apart).
- ECOG performance status will be assessed.
- A blood sample for safety laboratory assessments (haematology and clinical chemistry), including TSH (Part 1: and fT4) and urine sample for urinalysis will be collected. Blood sample for glycated hemoglobin (HBA1c) for patients with diabetes will be collected.
- A blood sample for determination of local PSA concentration will be collected (previous PSA value can be used as the baseline assessment if it was taken within 4 weeks prior to the start of the study treatment).
- A blood sample for local testosterone assessment will be collected.
- Radionuclide bone scan will be done and documented (prior bone scan can be used as the baseline assessment if it was performed within 4 weeks prior to the start of the study treatment).

- Chest, abdomen and pelvic CT or MRI will be done and documented (previous CT or MRI scans can be used as the baseline assessment if they were performed within 4 weeks prior to the start of the study treatment).
- Part 2 only: A non-mandatory symptom questionnaire will be introduced and instructed to the subject, and filled in by the subject. The symptom questionnaire will not be used in France. Applicable only to initial 40 patient cohort in Part 2/Phase 2 (excluding France).
- AEs, concomitant treatments (see section 5.7) and current medical conditions will be inquired.

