The clinical relevance of targeting androgen signalling in metastatic CRPC (mCRPC) is demonstrated by the survival advantage conferred by the newer AR-targeted agents abiraterone acetate (CYP17A1 inhibitor) in combination with prednisone and enzalutamide (AR antagonist). In abiraterone treated patients, up-regulation of CYP17A1, alternative ligand synthesis and AR splice variants are suggested as mechanisms for driving disease progression. The potent CYP17A1 inhibition leads to accumulation of upstream androgens, which may use alternate steroid synthesis pathway that ultimately leads to dihydrotestosterone (DHT) (Attard G et al., 2012). Recently also significant increases in the level of progesterone were reported in patients treated with abiraterone (Bertaglia V et al., 2017). Interestingly, the increased progesterone levels have been suggested to be one of the resistance mechanisms especially via mutated AR (Mostaghel EA et al., 2011, Sharifi N, 2015). It has also been suggested that long-term use of prednisone could lead a selection of AR mutations that are activated by prednisone leading to disease progression. In a retrospective small study in patients with CRPC (N=30), who have progressed on treatment with abiraterone and prednisone, a steroid switch to dexamethasone resulted in a  $\ge$  30% decline in prostate specific antigen (PSA) levels in 39.2% of patients and a median time to PSA progression of 11.7 weeks (Lorente D et al., 2014). However, as no mutational analyses were performed, a role of prednisone in disease progression remains speculative. Point mutations in the AR gene have been reported to occur at a comparatively high incidence in patients with mCRPC, especially in tumours progressing under the secondgeneration AR signaling inhibitors. Mutations in the AR may have various effects, including loss of function, increased or decreased AR signalling. Most of these mutations are located in the ligand-binding domain (LBD) of AR and appear to be somatic events. Gain-of-function mutations in the LBD of AR result in nonspecific activation of AR by weak androgens, progestins, glucocorticoids, estrogens and antiandrogens. One of the most frequently observed

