## 1.3.3 Potential risk associated with replacement therapy

Inhibition of CYP11A1 is anticipated to lead to deficiency in production of glucocorticoids and mineralocorticoids. Replacement therapy with glucocorticoid and mineralocorticoid is thus required with ODM-208 treatment.

It is expected that a significant proportion of patients have received corticosteroids for extended duration before entry to this study. Long-term use of moderate or high-dose corticosteroid doses (e.g.  $\geq 20$  mg prednisone daily) has a well-described adverse event (AE) profile including immunosuppression, hyperglycemia, myopathy, hypertension, osteoporosis, cataract, glaucoma, dyslipidemia, gastritis, and mood changes. Retrospective analyses of 2267 patients from phase III studies (COU-301-AA and COU-302-AA) showed that overall incidence of corticosteroid-associated AEs were low in mCRPC patients who used prednisone 5 mg twice daily with or without abiraterone. The most common AEs were hyperglycemia and weight increase. The frequency of corticosteroid-associated AEs remained low with increased duration of exposure to prednisone (Fizazi K et al., 2016). After discontinuation of the ODM-208 treatment, the glucocorticoid therapy will be gradually decreased with monitoring for adrenocortical insufficiency (see section 3.3.6.1).

To minimise risks related to over- or under-replacement with fludrocortisone close monitoring during the study will be done e.g. by measuring blood pressure (BP), serum electrolytes and

renin. If the dose is too low the patient might experience fatigue, postural hypotension/orthostatic dizziness, dehydration, hyperkalaemia and salt craving or if the dose is too high, the patient may experience hypertension, oedema/fluid retention, rapid weight gain and hypokalemia. Fluid retention and hypertension caused by hyperaldosteronism might lead to worsening of heart failure. After discontinuation of the ODM-208 treatment, the fludrocortisone therapy will be gradually decreased to avoid symptoms associated with mineralocorticoid deficiency.

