# 8.2 Estimation of sample size

No formal sample size calculation was performed. Separate dose escalation (3+3) will be performed in Part 1A Group 1 and Part 1A Group 2.

The purpose of the extension to the phase 2 expansion, introduced in Amendment 12, will be to achieve 2 cohorts of approximately 60 subjects per cohort under phase 2 conditions with and without AR LBD mutations to enable more accurate estimate of PSA response and rPFS, to support phase 3 study design as well as giving balance between the AR LBD mutation negative and positive patient population.

Simon's two-stage design (Simon R, 1989) was used to estimate the number of AR LBD mutation negative mCRPC patients in Part 2 extension (added in Amendment 12). The null hypothesis that the true PSA response rate is 5% will be tested against a one-sided alternative. Criteria for continuation of patient enrolment may be met at any time during the conduct of the study. However, if not met, then in the first stage, 23 subjects will be enrolled. If there are one or fewer PSA responses in these 23 subjects, the study will be stopped, otherwise, enrolment will continue as planned. The null hypothesis will be rejected if six or more PSA responses are observed in 56 patients. This design yields a significance level of 0.05 and power of 80% when the true response rate is 15%.

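### In Part 2, patients on another glucocorticoid change to dexamethasone on the day ODM-208 starts, so their PSA declines may be partly due to the switch

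*Protocol*

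**What the plan says.** - **Timing.** Under section 6.1.4, a patient with an ongoing glucocorticoid is to "continue the daily glucocorticoid intake during the whole screening period and to switch it to study replacement therapy on Day 1". Day 1 is also the day of the first ODM-208 dose.
- **What the switch is to.** In Part 2 (section 5.3.1.2), ODM-208 is taken "concomitantly with once daily oral dexamethasone 1.5 mg" as the recommended starting dose. In Part 1B the replacement may be "dexamethasone once daily or prednisone/prednisolone twice daily or hydrocortisone three times daily", so a change to dexamethasone is not general there.
- **Baseline.** Section 8.4 takes the last measurement before study treatment. For these patients that value is obtained on the old glucocorticoid.
- **Effect of a switch alone.** Section 1.1.1 describes patients "who have progressed on treatment with abiraterone and prednisone, a steroid switch to dexamethasone resulted in a" PSA decline of at least 30% "in 39.2% of patients and a median time to PSA progression of 11.7 weeks". The series was retrospective, with N=30.
- **Who is exposed.** Section 1.3.3 states: "It is expected that a significant proportion of patients have received corticosteroids for extended duration before entry to this study".
- **How PSA is used.** Antitumour activity is a primary objective of Part 2. Section 8.4.3.1.1 counts declines of 30% and 50% and best response. For the mutation-negative cohort, section 8.2 says: "The null hypothesis that the true PSA response rate is 5% will be tested against a one-sided alternative". That cohort stops at one or fewer responses in 23 patients, and the null is rejected at six or more in 56.
- **Presentation.** Results are split by study part, dose level and AR LBD mutation status (section 8.4).

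**The concern.** For a patient who enters on prednisone, two things change on Day 1: ODM-208 begins and the glucocorticoid becomes dexamethasone. The protocol's own background says the second change alone can lower PSA. With no control group and a baseline that precedes both changes, a PSA decline in such a patient cannot be assigned to one or the other.

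The 30% threshold and best response are most exposed. The cited switch effect was measured at 30%, and its median time to PSA progression was 11.7 weeks. That is longer than the minimum 8 weeks of follow-up required before the mutation-negative interim look (section 8.5).

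Two readings are at stake. One is the Part 2 PSA response rate, which is meant to inform the phase 3 design. The other is the mutation-negative decision rule, whose error rate of 0.05 holds only if 5% is the true response rate in the absence of ODM-208 activity.

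**Working it through.** **Inputs from the protocol.** Stage 1 has n = 23 and stops at ≤1 response; the final rule rejects at ≥6 of 56; null 5%, alternative 15%, significance level 0.05, power 80% (section 8.2).

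**Inputs not in the protocol, so assumed.** f is the share of patients switched from another glucocorticoid to dexamethasone on Day 1 (10%, 30%, 50%). q is the chance that the switch alone gives a PSA response as the rule counts it (10%, 20%, 30%).

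**Step 1: reproduce the stated design.** The rejection probability at true rate p is the sum over x = 2 to 23 of P(X₁ = x) × P(X₂ ≥ 6 − x), with X₁ ~ Bin(23, p) and X₂ ~ Bin(33, p). At p = 5% it is 0.050; at p = 15% it is 0.800. Both stated figures are right.

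**Step 2: add a switch effect, under two readings of the 5% null.**

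*Reading A.* Unswitched patients respond at 5% and ODM-208 adds nothing in switched patients, so p = f·q + (1 − f)·0.05. Example: 0.30 × 0.20 + 0.70 × 0.05 = 0.095.

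*Reading B.* ODM-208 is inert and the 5% null is meant to include any switch effect, so p = f·q. Example: 0.30 × 0.20 = 0.06.

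| f | q | p (A) | Reject (A) | p (B) | Reject (B) |
|---|---|---|---|---|---|
| 10% | 10% | 5.5% | 0.07 | 1% | <0.001 |
| 30% | 10% | 6.5% | 0.13 | 3% | 0.005 |
| 30% | 20% | 9.5% | 0.39 | 6% | 0.10 |
| 30% | 30% | 12.5% | 0.65 | 9% | 0.34 |
| 50% | 10% | 7.5% | 0.21 | 5% | 0.05 |
| 50% | 20% | 12.5% | 0.65 | 10% | 0.43 |
| 50% | 30% | 17.5% | 0.90 | 15% | 0.80 |

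**Step 3: how far the 39.2% carries.** It is a rate of ≥30% declines, so it bears directly on the PSA30 table. It is not an estimate of q at the 50% threshold, and the protocol gives none. It is also imprecise: 39.2% of 30 is 11.8 patients, so the exact count is unclear. With 12 of 30 the exact 95% interval would be about 23% to 59%.

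**The case against.** Several points on the other side stand.

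- **Share switched.** Section 1.3.3 speaks of patients who have received corticosteroids, not of patients still on a non-dexamethasone glucocorticoid the day before Day 1. Section 6.1.4 is conditional, abiraterone must have stopped at least two weeks earlier, and patients already on dexamethasone do not change agent. The share may be small, and at 10% switched with a 10% switch response the error is 0.07.
- **Transfer of the 39.2%.** It comes from a small retrospective series of one patient type. Part 2 enrols after any novel AR-targeted therapy plus a taxane. Section 8.2 does not define PSA response; where section 1.1.1 attaches a threshold to that term, it is 50%.
- **Meaning of the null.** If the 5% is meant to include the switch effect, the inflation shrinks or disappears at low f and q.
- **Scope of the claim.** Replacement is required with ODM-208, so what is tested is always the combination. Activity is also read from ORR, rPFS, CTC response and survival.
- **Place of the table.** Detailed subgroup tables often sit in the SAP, which was not available here. The absence of such a table from the protocol is therefore not the finding. The finding is the simultaneous start with a baseline before both changes.

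The protocol calls prednisone's role speculative, but that concerns its part in disease progression. The same passage still attributes the PSA declines to the switch.

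A reader might infer that switch responses will certainly be counted as ODM-208 responses, or that PSA30 says nothing about ODM-208. The documents do not support either, because the share switched is unknown and unswitched patients remain informative. A reader might also infer that the mutation-positive versus mutation-negative contrast is distorted. Section 1.1.1 links abiraterone plus prednisone to some AR mutations, but nothing shows that the share switched differs between the cohorts.

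**Conclusion.** The point holds as an upward bias of unknown size in the Part 2 PSA results of patients who change to dexamethasone on Day 1. It is strongest for PSA30 and best response. At the 12-week readout it may have partly faded, given the cited 11.7-week median time to PSA progression.

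The two-stage arithmetic is correct; what is uncertain is whether 5% represents the response rate without ODM-208 activity. The rejection probabilities are illustrations resting on an assumed share switched, an assumed switch response and a chosen reading of the null. They run from close to nominal (or well below it under reading B) to 0.90 under reading A and 0.80 under reading B. They do not show that the mutation-negative test is invalid. They show that a positive result could not be attributed to ODM-208 alone without knowing how many responders were switched. A protocol change is worthwhile because the results feed phase 3 planning and the remedy is cheap.

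**What to change.** 1. In section 8.4.3.1.1, present Part 2 PSA30, PSA50 and time to PSA progression by glucocorticoid in use on the day before Day 1 (none; prednisone or prednisolone; dexamethasone; other), overall and by AR LBD mutation status.
2. In section 8.2, add a sensitivity reading of the mutation-negative PSA response that excludes patients switched from another glucocorticoid to dexamethasone on Day 1.
3. Describe the PSA result as activity of ODM-208 plus dexamethasone, unless the unswitched patients support a claim for ODM-208 itself.

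The cost is protocol or SAP wording, one table and one sensitivity reading. Section 5.7 already requires prior prostate cancer therapy, and concomitant treatments from consent onward, to be recorded. The downside is small subgroups and a more cautious claim. No change to treatment is proposed.
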